We will undertake a study with 20 patients with biochemical recurrence of prostate cancer status post radical prostatectomy. Consideration for inclusion in this study will be based on detectable PSA after radical prostatectomy (PSA ≥ 0.1 ng/ml). Histology proof of recurrence will not be required. All patients will be recruited from the radiation oncology unit and other oncology units under Emory Healthcare. All 20 patients will undergo two sets of ^{18}F -rhPSMA-7.3 PET/CT scans, one with and the other without intravenous administration of 20 mg of furosemide at the time of radiotracer injection. All patients will have oral hydration with 500 to 1000 ml of water during the uptake phase. The first set of 10 patients will have a ^{18}F -rhPSMA-7.3 PET/CT without-furosemide followed by a ^{18}F -rhPSMA-7.3 PET/CT with-furosemide 2-7 days afterward. The second set of 10 patients will have their two ^{18}F -rhPSMA-7.3 PET scans in the reverse order, with-furosemide first followed by without-furosemide 2-7 days afterward. Vital signs will be measured before and after each radiotracer administration. Each patient will undergo both imaging techniques, and the results will be interpreted blindly. A minimum of 2 days is required between the two ^{18}F -rhPSMA-7.3 to allow for the complete decay of the radiotracer from the first scan before the second scan (physical half-life of ^{18}F is 110 minutes). Patients will be allowed to void during the 60-70 minutes uptake period between ^{18}F -rhPSMA-7.3 radiotracer administration and the commencement of PET/CT imaging. Patients will be encouraged to void at approximately 50 minutes post injection and encouraged to refrain from voiding 15 minutes before the commencement of the PET/CT (60-70 min post injection), if possible, to facilitate bladder distension.

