Two nuclear medicine physicians, Drs. [name] and [name], who are coinvestigators in this work, will independently interpret the two scans of the entire 20 patients within 2 weeks of completion of the 2nd PET/CT for each patient. The readers will be blinded to all imaging and furosemide administration, including the other PET/CT done as part of the study. All suspicious lesions with non-physiologic activity above background for loco-regional spread and distant disease will be identified and rated for suspicion of malignancy on a 5-point Likert scale (where 1 = definitely benign and 5 = definitely malignant). Image interpretation will be done on an advanced workstation (MIM Software). Metabolic parameters (SUV max, SUV mean, SUVpeak of all identified lesions with be determined and recorded. The bladder volume on each scan will be determined and recorded. SUV max and SUV mean of background organs, including the parotid, aortic arch, liver, spleen, kidney, ureters and the urinary bladder, will be determined and recorded. The presence and degree of dropout or halo artifacts around the bladder and kidney will also be recorded. After the individual blind reads, the two readers will perform an unblinded consensus read for the reconciliation interpretation of the two scans for each patient. Concordant and discordant lesions between each PET/CT study and conventional imaging will be reported.

Scientific Rationale for Study Design

Our preliminary data support a key scientific premise that the intravenous administration of furosemide at the time of radiotracer injection leads to lower radiotracer concentration in the urinary bladder. This finding is supported by published studies in the literature showing that intravenous administration of furosemide at the time of ^{68}Ga -PSMA-11 administration causes a reduction in bladder activity,

Protocol Title: Strategy to Reduce Bladder Activity with rhPSMA 7.3: Comparison of 18F-rhPSMA 7.3 PET/CT with and without Furosemide in Biochemical Recurrence of Prostate Cancer

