Two nuclear medicine physicians, Drs. [name] and [name], who are coinvestigators in this work, will independently interpret the two scans of the entire 20 patients. The readers will be blinded to all imaging and furosemide administration, including the other PET/CT done as part of the study. All suspicious lesions with non-physiologic activity above background for loco-regional spread and distant disease will be identified and rated for suspicion of malignancy on a 5-point Likert scale (where 1 = definitely benign and 5 = definitely malignant). Image interpretation will be done on an advanced workstation (MIM Software). Metabolic parameters (SUV max, SUV mean, SUVpeak of all identified lesions with be determined and recorded. The bladder volume on each scan will be determined and recorded. SUV max and SUV mean of background organs, including the parotid, aortic arch, liver, spleen, kidney, ureters and the urinary bladder, will be determined and recorded. The presence and degree of dropout or halo artifacts around the bladder and kidney will also be recorded. After the individual blind reads, the two readers will perform an unblinded consensus read for the reconciliation interpretation of the two scans for each patient. Concordant and discordant lesions between each PET/CT study and conventional imaging will be reported.

Scientific Rationale for Study Design

Our preliminary data support a key scientific premise that the intravenous administration of furosemide at the time of radiotracer injection leads to lower radiotracer concentration in the urinary bladder. This finding is supported by published studies in the literature showing that intravenous administration of furosemide at the time of 68Ga-PSMA-11 administration causes a reduction in bladder activity, improves detection of local prostate bed recurrence, and improves reader confidence. We hypothesize that the administration of intravenous furosemide at the time of radiotracer injection will reduce the activity of 18F-rhPSMA-7.3 in the urinary bladder and facilitates the identification of prostate bed recurrence in men with rising serum PSA post-prostatectomy. We also hypothesize that reduced urinary activity of 18F-rhPSMA-7.3 will improve readers' confidence in assessing prostate bed recurrence of prostate cancer. An improved lesion detection will influence management decisions.

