The study will be closed to recruitment once all 20 patients have been recruited, scanned with the 2 PET/CTs each and have completed follow-up (1-3 business days after each PET/CT). The study will be formally closed once all manuscripts have been published and all follow-up completed. There will be no other study-specific visits after the second PET/CT scan (visit 2), though the patient will be called by the study nurse within 1-3 business days after each study to ensure no delayed AEs occurred. The follow-up phone call for one study will be performed before the patient undergoes the subsequent scan.

3. Sharing of Results with Participants

PET findings will be used for research purposes within the context of the clinical trial as noted above. The key findings of the PET/CT and all incidental findings will be recorded in the clinical research form and emergent incidental findings will be communicated to the patient's physician who is also an investigator in this study. The non-emergent findings will be conveyed to the patient at the discretion of the patient's physician after a discussion of the risk versus benefit since this investigational radiotracer is not FDA approved for clinical use.

Incidental Findings

- a. All incidental findings noted by the imager will be discussed with the attending physician who is a co-investigator and documented in the electronic medical record.

Protocol Title: Strategy to Reduce Bladder Activity with rhPSMA 7.3: Comparison of 18F-rhPSMA 7.3 PET/CT with and without Furosemide in Biochemical Recurrence of Prostate Cancer

- b. The oncologist will educate the patient about the nature of the incidental finding, how to seek care from a clinician or specialist, obtaining health insurance to secure treatment, and/or referral to a clinical specialist, if one is required.
- c. Language to this effect is present in the consent form.

4. Study Timelines

The total duration of the study is 5 years, with an accrual rate of approximately 4 patients per year. For the individual study participant, the patient participation is complete after the 2nd PET/CT study. However, the participating patients may be followed up for correlation for up to 5 years after the study.

5. Inclusion and Exclusion Criteria

Adult patients with biochemical recurrence of prostate cancer, status post prostatectomy who meet the eligibility criteria will be enrolled in the study.

Inclusion Criteria

Adenocarcinoma of the prostate, post-prostatectomy.

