Bladder and renal activity: Change in bladder and renal activity, as measured by bladder SUV max, bladder volume, and renal SUV mean/max, between administration of 20mg furosemide IV at the time of radiotracer injection and without furosemide will be assessed using paired t-tests, or using non-parametric equivalents such as a Wilcoxon signed rank tests. Descriptively, bladder and renal activity will be reported for those administered 20mg furosemide IV at the time of radiotracer injection first (Group A), and those administered 20mg furosemide IV at the time of radiotracer injection second (Group B).

Recurrent disease rate: Recurrent disease is defined as presence of unequivocal soft tissue radiotracer uptake that is characteristic of malignancy in the prostate bed and/or surrounding soft tissues and within pelvic lymph nodes. Recurrent disease rates will be compared (furosemide vs. non-furosemide 18F-rhPSMA-7.3 PET scans using McNemar's tests. Rates will be reported, along with 95% exact confidence intervals using the Clopper-Pearson method. Descriptively, recurrent disease rate will be reported for those administered 20mg furosemide IV at the time of radiotracer injection first (Group A), and those administered 20mg furosemide IV at the time of radiotracer injection second (Group B).

Confidence score: The readers' confidence in identifying prostate bed, pelvic and retroperitoneal nodal disease and other recurrence on 18F-rhPSMA-7.3 PET/CT with furosemide compared with the 18F-rhPSMA-7.3 PET/CT without furosemide will be scored using a 5-point Likert scale. This analysis will be descriptive, with summary statistics reported with and without furosemide.

Safety Analyses: Not applicable.

Baseline Descriptive Statistics

Patient characteristics will be summarized descriptively, using mean, median, interquartile range, min/max, and standard deviation for continuous variables, and using frequencies and percentages for categorical variables.

Interim Analysis: N/A

16.2 Data/specimens:

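### Readers are declared blind to a patient's other scan, but nothing in the reading schedule secures that blinding against recall

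*Combined protocol and SAP*

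**What the plan says.** Under Procedures Involved (Overall Design), two nuclear medicine physicians who are co-investigators "will independently interpret the two scans of the entire 20 patients within 2 weeks of completion of the 2nd PET/CT for each patient". The next sentence states the blinding: "The readers will be blinded to all imaging and furosemide administration, including the other PET/CT done as part of the study". Section 5.7, Description of Study Procedures, gives the same account without the two-week limit: the readers "will independently interpret the two scans of the entire 20 patients. The readers will be blinded to all imaging and furosemide administration".

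Both sections place the reconciliation afterwards: "After the individual blind reads, the two readers will perform an unblinded consensus read". The two scans are 2 to 7 days apart, in either order, with 10 patients in each order. Study Timelines describes accrual: "The total duration of the study is 5 years, with an accrual rate of approximately 4 patients per year".

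The reads supply two secondary comparisons. Objective 1 compares detection on blinded interpretations. For it, section 11.1 states "Recurrent disease rates will be compared" between the two scan types with McNemar's test. Objective 2 compares reader confidence on a five-point scale, and section 11.1 makes this descriptive only.

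The documents give no minimum time between one reader's two reads of a patient, no coding of scans, no random reading order, no lock on the first form, and no separate reader for each scan.

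**The concern.** The two scans show the same man within a week, with the same anatomy and largely the same disease. A reader who has just mapped his lesions on one scan brings that map to the other. Withholding the other scan and the furosemide assignment does not remove this, because the reader has already read the other scan.

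The likely effect is that a lesion called on the first read is looked for, and scored with more confidence, on the second. Pairs that would have disagreed then agree. McNemar's test takes all its information from disagreeing pairs, so the detection comparison moves towards no difference, and the confidence scores move together. Nothing in the planned analysis would show that this had happened, and after the reads only re-reading could repair it.

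This is a matter of memory for lesions. It is separate from whether the appearance of the bladder reveals which scan had furosemide.

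**Working it through.** **Inputs from the documents.** Scan interval 2 to 7 days and 10 patients per order (Overall Design); reading deadline 14 days after the second scan (Procedures Involved only); accrual about 4 per year (Study Timelines); 20 pairs, McNemar's test, two-sided alpha 0.05 (section 11.1). **Assumed here:** Poisson arrivals, the true discordance rates, and the share of discordant pairs that recall removes.

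**1. The plan's own figure.** The only power statement concerns the primary endpoint. With n = 20, a difference of 9.2 − 2.6 = 6.6 and the stated SD of change of 10, the noncentrality is 0.66 × √20 = 2.95, and the two-sided paired t-test has 79.9% power. The stated 80% is reproduced from the plan's inputs. It rests on a bladder measurement and uses no lesion call, so recall of lesions does not touch it. The plan gives no figure for the reader endpoints.

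**2. Gap between a reader's two reads.** Minimum: 0 days, since one session complies. Maximum, if scan 1 is read on its own day and scan 2 on the last permitted day: 2 + 14 = 16 to 7 + 14 = 21 days. If both reads wait for the second scan, the maximum is 14 days. Any longer washout breaks the deadline in Procedures Involved but not the text of section 5.7.

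**3. Study cases that could fall between the reads.** Probability of at least one other patient = 1 − exp(−4 × days/365).
- 14 days: 1 − exp(−0.153) = 14%
- 21 days: 1 − exp(−0.230) = 21%

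So trial cases can seldom be interleaved to dilute memory.

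**4. Sensitivity of the detection test.** If all k discordant pairs point one way, the exact two-sided p-value is 2 × 0.5^k: 0.0625 for k = 5 and 0.031 for k = 6. At least 6 discordant pairs are needed. The table gives exact McNemar power with 20 pairs; discordance and share removed are illustrative only.

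| Assumed true discordance (one way vs other) | No recall | 25% of discordant pairs removed | 50% removed |
|---|---|---|---|
| 30% vs 0% | 58% | 28% | 7% |
| 35% vs 5% | 46% | 27% | 9% |

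In the first row, the expected number of discordant pairs falls from 20 × 0.30 = 6.0 to 4.5 and 3.0. If recall only carries positives forward, and the positive scan is read first in half of the discordant pairs, 50% is the ceiling.

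The only detection contrast in the documents is 25.5% vs 17.3% (Background; another tracer, separate patient groups), a difference of 8.2 points. Taken as 8.2% vs 0%, or 13.2% vs 5%, it gives at most 2% power even without recall.

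**5. Direction.** If scans are read in acquisition order, the later scan is with furosemide in 10 patients and without in 10. A gain to the later scan therefore enters with opposite signs and roughly cancels between conditions. What remains is attenuation.

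**The case against.** The plan states the blinding explicitly, twice, and silence on a minimum gap is not an instruction to read the scans together. A reader of the protocol might infer that back-to-back reading is required, or that the second read is by design unblinded. The documents support neither: the deadline is only a latest date, up to 16 to 21 days is possible, and section 5.7 has no deadline. That objection stands. What survives it is that the blinding is stated and not secured.

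A reader might also infer that recall favours one condition. The 10/10 split of scan order answers this, at least for reads in acquisition order.

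The size can fairly be challenged too. Nothing in the documents says how often a lesion is carried over. Section 11.1 requires unequivocal uptake, and memory does not readily make obscured uptake unequivocal. A remembered negative, or bladder activity that reveals the furosemide scan, could act differently. The readers' other clinical work may also separate the reads; the documents do not say. All of this stands, and it rules out quoting a number of lost discordant pairs.

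Finally, the stakes are limited. Confidence is not tested, and detection has little power at modest differences anyway. With a 4–0 split, for example, exact McNemar gives p = 0.125, and with 3–0 it gives 0.25, so losing one such pair changes no conclusion. Section 11.1 does not name the version; the uncorrected asymptotic test would move from 0.046 to 0.083. This lowers the priority. It does not make the reads blind to each other.

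**Conclusion.** The point holds as a weakness in how the blinding is protected, confined to the two secondary reader comparisons. The same readers read both scans. The deadline in Procedures Involved allows a zero gap and rules out one longer than 16 to 21 days, and no coding, order or lock compensates. Other study cases intervene in only about 14% (14 days) to 21% (21 days) of windows, given Poisson arrivals at the planned rate. The two descriptions of the reads also differ on the deadline and must be reconciled.

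The most plausible consequence is attenuation, so a finding of no difference in detection or confidence could not be separated from recall. The documents do not allow that attenuation to be sized; the power figures above are illustrations under assumed rates. They do not support a claim that recall favours furosemide, or that the primary result is at risk. The change is a cheap improvement and worth making before reads begin.

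**What to change.** Put one identical text in Procedures Involved and in section 5.7:

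- For each patient, randomise which scan reader 1 reads first; reader 2 reads the other scan first. Both first reads are done within 2 weeks of the second scan.
- Lock lesion calls and Likert scores for these reads.
- Each reader then reads the remaining scan under a new code, without access to the first form, after a pre-stated washout longer than the present window allows. Six weeks is an example; the length is a design choice and has no basis in the documents.
- Hold the consensus read only after all blinded forms for the patient are locked. The plan already places consensus after the blind reads, so only the lock is new.
- Record both read dates on the form.

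Crossing the readers matters. If each reader's first scan were drawn independently, both would draw the same scan half the time, and the other would go unread through the washout. Sharing of Results with Participants requires incidental findings to be recorded and emergent ones passed on. With crossed first reads, each scan is seen by one reader within 2 weeks.

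The cost is protocol wording, a randomised reading list and two date fields. The readers are the same, and so is the number of reads (2 readers × 2 scans × 20 patients = 80). The downside is that the second reads and the consensus come some weeks later, which is small in a 5-year study. The change reduces recall; it does not raise the low power of the detection comparison.

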
Secondary
 
1. To compare detection rates of recurrent disease in blinded interpretations between the furosemide and non-furosemide ¹⁸F-rhPSMA-7.3 PET/CT scans, with patients serving as their own internal controls
 
Lesion detection rates on a patient and region basis will be recorded in addition to the ratio of
	Compare lesion detection and confidence between rhPSMA7.3 PET without and with furosemide

OBJECTIVES	ENDPOINTS

the lesion to background activity including blood pool, liver, spleen and parotid. Test retest of lesions and background measurements between the studies with furosemide and without furosemide will be performed.
 
2. To compare reader confidence in identifying prostate bed and other recurrent lesions on a 18F-rhPSMA-7.3 PET/CT with furosemide compared with 18F-rhPSMA-7.3 PET/CT without furosemide
 
The readers' (total two readers) confidence in the assessment of findings in the prostate bed and other locoregional and distant lesions will be rated using a five-point Likert scale with 1 being definitely benign and 5 being definitely malignant. The readers' confidence scores for both the PET/CT scans (with and without furosemide) will be compared. The readers will be blinded to the furosemide injection.
	
Tertiary/Exploratory	

2. Background

Prostate cancer is the most common cancer diagnosed in men in 2021 and accounted for 11% of all cancer-related deaths in men in the United States. Early diagnosis is desirable so that definite treatment with curative intent can be offered. RP is a suitable definitive therapy offered to patients with early-stage disease. Complete tumor resection during RP with or without pelvic lymph node dissection results in serum PSA level decline below detectable limits. PSA can then subsequently be used as a sensitive and specific tumor marker in the early detection of disease recurrence. The American Urological Association and European Association of Urology guidelines define biochemical recurrence after RP as an initial PSA value of 0.2 ng/mL or greater, measured 6 weeks after surgery to allow appropriate washout of any residual PSA. This result is confirmed by a subsequent PSA value of 0.2 ng/mL or greater to rule out a laboratory error[1, 2]. The risk of biochemical recurrence is associated with the baseline risk categorization of the disease, with patients in higher-risk groupings having

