Efforts are ongoing towards improving the detection rates of PSMA targeted imaging of BCR of prostate cancer. The desirable radioligand should preferably be labeled to F-18 and have low renal excretion into the urinary bladder. ¹⁸F-PSMA-1007 is a PSMA ligand labeled with F-18 and is excreted mostly via the biliary route. While these kinetic characteristics make it suitable, especially in the assessment of prostate bed recurrence, a high incidence of non-specific ¹⁸F-PSMA-1007 uptake especially in bones leading to a high false positivity rate has been a significant drawback[7, 8]. Radiohybrid (rhPSMA) is a new class of PSMA-targeting radioligand. rhPSMA ligands are not only suitable for labeling with F-18, but the molecule can be labeled with diagnostic and therapeutic radiometals[9, 10]. Coming in the wake of the recent FDA approval of PSMA-targeted radionuclide therapy for metastatic castration-resistant prostate cancer (mCRPC), rhPSMA is a true theranostic agent where the same molecule labeled with a diagnostic radionuclide such as F-18 can be used for imaging and labeled to a therapeutic radionuclide such as Lutetium-177. In a recent study of 261 patients with BCR of prostate cancer after RP and a median serum PSA level of 0.96 ng/mL, ¹⁸F-rhPSMA-7 PET/CT detected disease recurrence in 81% of patients. Stratified according to serum PSA levels, the detection rates were 71%, 86%, 86%, and 95% at PSA levels of 0.2 to <0.5 ng/mL, 0.5 to <1 ng/mL, 1 to <2 ng/mL, and ≥2 ng/mL, respectively[11]. There are four stereoisomers of rhPSMA-7, of which rhPSMA-7.3 has shown to be the preferred molecule based on its higher uptake in tumor, lower uptake by the kidneys, and improved clearance from the background[12]. In a single-center retrospective review of 242 patients with a median PSA level of 0.6 ng/mL who were imaged with ¹⁸F-rhPSMA-7.3 PET/CT for the localization of the site of recurrence of prostate cancer, Rauscher and colleagues reported an overall positivity rate of 72.7%. At serum PSA levels of 0.2 to <0.5, 0.5 to <1, 1 to <2, and ≥2 ng/mL, lesion detection rates were 61.8%, 67.9%, 81.1%, and 95.7%, respectively[13]. Based on the encouraging diagnostic performance of ¹⁸F-rhPSMA-7.3 PET/CT for the localization of BCR of prostate cancer, prospective trials have been undertaken to confirm these earlier results. In a phase 1 trial evaluating the safety, biodistribution, and radiation dosimetry of ¹⁸F-rhPSMA-7.3 in healthy adult volunteers, Tolvanen and colleagues reported that ¹⁸F-rhPSMA-7.3 was well tolerated in all volunteers (a single case of mild headache not requiring medication for treatment was judged to be due to rhPSMA-7.3 injection while others were not) with a calculated effective dose of 0.0141 mSv/MBq, which is lower compared to effective dose due of other PSMA ligands [10]. ¹⁸F-rhPSMA-7.3 showed a urinary route of excretion with bladder activity seen from 7 minutes post tracer injection,

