
which increased progressively thereafter. The renal urinary excretion of ¹⁸F-rhPSMA-7.3 was lower compared with excretion of other PSMA ligands such as ⁶⁸Ga-PSMA-11 and ¹⁸F-DCFPyL, but higher than that of ¹⁸F-PSMA-1007[10]. Continued effort geared towards a further reduction in the urinary excretion of ¹⁸F-rhPSMA-7.3 is pertinent to improve detection rates.

Forced diuresis with co-administration of furosemide and the radiotracer is a strategy that has been explored in decreasing the urinary activity of other PSMA radioligands with a urinary route of excretion. In a study comparing the local prostate bed recurrence detection between patients who received hydration and furosemide administration at the time of ⁶⁸Ga-PSMA-11 injection versus patients who did not, Uprimmy et al. reported a higher local prostate bed recurrence detection in patients who received hydration with intravenous furosemide versus patients who did not (25.5% versus 17.3%, p=0.048)[14]. The frequency of equivocal findings for prostate bed recurrence was more prevalent among patients who did not receive furosemide injection compared with those who did (16.8% versus 12.3%). Lower urinary activity did not influence the intensity of tracer uptake in prostate cancer recurrent lesions between the two groups with comparable SUV max in recurrent lesions. Similar improved diagnostic confidence with the assessment of disease in the prostate bed has been reported in other studies[15]. In an analysis of data from Technical University of Munich, a cohort of 17 patients imaged with ¹⁸F-rhPSMA-7 (White Paper Prepared for Syncona: Evaluation of ¹⁸F-rhPSMA7, Unpublished) demonstrated bladder SUVmean mean (SD) (range): 4.57 (6.4) (1.4-28.8). Yet as shown in a subanalysis, this lower bladder activity is highly dependent on the use of furosemide. Mean bladder SUV mean (n=5) without furosemide is 9.24, while with furosemide (n=12), bladder SUVmean is 2.63. In the joint guidelines of the European Association of Nuclear Medicine (EANM) and the Society of Nuclear Medicine and Molecular Imaging (SNMMI), the use of furosemide was recommended for ⁶⁸Ga-PSMA-11 PET/CT imaging of prostate cancer[16].

2.3 3.1 Study Rationale

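### The only scoring rule covers lesions a reader marks, so the confidence summaries with and without furosemide can rest on different lesions and men, and a prostate bed read as clear may have no confidence value

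*Combined protocol and SAP*

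**What the plan says.** Four places bear on the confidence score.

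- **Section 3, Procedures Involved, Overall Design.** "All suspicious lesions with non-physiologic activity above background for loco-regional spread and distant disease will be identified and rated for suspicion of malignancy". The scale runs 1-5. After the independent blinded reads, the same two readers hold an unblinded consensus read of both scans.
- **Section 5.7, Overall Design.** The rule is repeated: lesions "will be identified and rated for suspicion of malignancy on a 5-point Likert scale (where 1 = definitely benign and 5 = definitely malignant").
- **Section 2, Objectives (and Endpoints), secondary objective 2.** The wording here is: "confidence in the assessment of findings in the prostate bed and other locoregional and distant lesions will be rated using a five-point Likert scale". The anchors are the same, and the scores for the two scans are to be compared.
- **Section 11.1, Analysis of the Secondary Endpoints, Confidence score.** What is scored is "confidence in identifying prostate bed, pelvic and retroperitoneal nodal disease and other recurrence on 18F-rhPSMA-7.3 PET/CT with furosemide" against the scan without it. Then: "This analysis will be descriptive, with summary statistics reported with and without furosemide".

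For detection, secondary objective 1 does state a unit: "Lesion detection rates on a patient and region basis will be recorded". No such statement is made for confidence. Nothing gives a value for a region without a finding, matches lesions or regions across the two scans, or defines which men enter each summary.

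**The concern.** The design's strength is that each man is his own control. For confidence, that holds only if the same regions in the same men are scored under both conditions. Under a marked-lesion rule, a score exists only if the reader saw something suspicious on that scan. The Study Rationale (3.1) hypothesises that furosemide makes prostate bed recurrence easier to identify, so the existence of a score is itself expected to depend on furosemide.

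Three ordinary situations have no rule: no lesion marked on either scan, a lesion marked on only one, and a region read as clear. The third matters most. A bed that was obscured by bladder activity and becomes confidently clear is a gain the objective seeks, yet it adds nothing to the furosemide summary.

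The timing also matters. Once the unblinded consensus read has taken place, the readers' blinded confidence about clear regions in that man cannot be recovered.

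**Working it through.** The plan states no sample size, precision or expected value for the confidence score, so there is no figure of its own to reproduce. The counts below are illustrations from rates in Section 2, Background.

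**Inputs**
- Patient-level positivity with rhPSMA-7.3: 72.7% overall, 61.8% at PSA 0.2 to <0.5 ng/mL. Both are rates for a single scan.
- Local recurrence detected: 25.5% with furosemide, 17.3% without. Equivocal bed findings: 12.3% with, 16.8% without. These come from 68Ga-PSMA-11 in separate patient groups.
- N = 20 men, two scans each.
- Assumption for the bed: equivocal findings are marked and do not overlap with positive ones.

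**1. Men with no positive lesion**
- On a given scan: 20 × (1 − 0.727) = 5.5. At the 61.8% rate: 20 × 0.382 = 7.6.
- On both scans, at 72.7%: at most 5.5, reached only if the two scans agree perfectly. Independence would give 20 × 0.273² = 1.5. Marked equivocal lesions would lower all of these.

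**2. Beds with a score**
- With furosemide: 0.255 + 0.123 = 0.378, so 20 × 0.378 = 7.6 scored and 12.4 not.
- Without: 0.173 + 0.168 = 0.341, so 20 × 0.341 = 6.8 scored and 13.2 not.
- Men scored on both: between 20 × max(0, 0.378 + 0.341 − 1) = 0 and 20 × 0.341 = 6.8. Scoring every bed gives 20 pairs per reader.

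**3. Which way the unmatched comparison can move**
- Hypothetical: six lesions score 4 without furosemide. With it, two of them rise to 5, a matched change of 26/6 − 4 = +0.33. If furosemide also reveals two lesions scored 3, the difference in summary means is (26 + 6)/8 − 4 = 0.00. With three such lesions it is (26 + 9)/9 − 4 = −0.11.
- With the Background bed rates and assumed scores of 5 for positive and 3 for equivocal, the marked-only means are (0.255 × 5 + 0.123 × 3)/0.378 = 4.35 with and (0.173 × 5 + 0.168 × 3)/0.341 = 4.01 without, a difference of +0.33. Counting every unmarked bed as 1 gives 2.27 and 2.03, a difference of +0.24.

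So the summary can understate, reverse or overstate the change, depending on what is newly seen.

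**4. Whether the raw mean would measure confidence if every bed were scored**

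Take 20 beds: three 5s, three 3s, fourteen 1s. Then let two beds scored 3 become confidently clear (1).

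| Summary | Before | After |
|---|---|---|
| Mean score | (15 + 9 + 14)/20 = 1.90 | (15 + 3 + 16)/20 = 1.70 |
| Mean of \|score − 3\| | (6 + 0 + 28)/20 = 1.70 | (6 + 0 + 32)/20 = 1.90 |
| Share scored 3 | 3/20 = 15% | 1/20 = 5% |

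Certainty rose. The mean score falls, while the other two summaries move the right way. The scale runs from benign to malignant, so it rates suspicion; certainty lies at both ends.

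**The case against.** The best defence is that region scoring is intended. The Overall Design text calls its rating one of suspicion and never names it the confidence score, while Section 11.1 lists the prostate bed, pelvic and retroperitoneal nodes and other sites. That is a fair reading, and it rules out saying that the plan forbids region scores. It does not close the gap: naming regions in which disease may be identified does not tell a reader to score a clear one. The objectives table uses the same five-point scale and anchors as the lesion rule, and the plan states a region basis where it means one, for detection.

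Other parts of the defence limit the point:

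- A reader might infer that a clear bed leaves no data at all. Detection is recorded by region and halo artifacts are recorded too; only the confidence value is missing.
- A reader might infer that 27.3% of men would have no score on either scan. The 72.7% is a per-scan rate, so that figure is a ceiling.
- A reader might infer that furosemide's mean confidence will be pushed down by newly seen equivocal lesions. The cited study found fewer equivocal bed findings with furosemide, and its rates give a rise.
- A reader might size the loss as a ratio of standard errors. No test or interval is planned for this endpoint, and filling in clear regions would change the SD, so such a ratio measures nothing in the plan.

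**Conclusion.** The concern holds as a gap in the scoring rule and the unit of analysis. Followed as written, the plan can compare confidence over different, furosemide-dependent sets of lesions and men, and it collects no confidence value for a bed read as clear.

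On the illustrative rates, about 7.6 and 6.8 of 20 scans would carry a bed score, and no more than 6.8 men would have one on both, against 20 pairs with full scoring. These counts rest on another tracer, unpaired groups and the marking of equivocal findings; they show scale and are not forecasts. The documents do not establish the direction of any distortion.

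The endpoint is secondary and descriptive, so neither the primary conclusion nor any error rate is affected. The change is still worth making, because this is one of only two secondary objectives and the missing blinded scores cannot be recovered later.

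**What to change.** In secondary objective 2, both Overall Design sections (3 and 5.7) and the Confidence score paragraph of 11.1:

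1. Each blinded reader gives one 1-5 score to every prespecified region (prostate bed, pelvic nodes, retroperitoneal nodes, other) on every scan, including regions with no suspicious uptake. The reader should enter the score actively, not have it default to 1, so that an obscured bed can be recorded as uncertain.
2. Summarise confidence as within-patient paired changes in |score − 3|, or in the share of regions scored 3, by region and by reader over all 20 pairs. Do not use the raw mean score as the measure of confidence.
3. Report scores of individual lesions as supportive, with the number of men who have a marked lesion on both scans, one scan or neither.

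The cost is CRF and SAP wording and four region scores per read: 20 men × 2 scans × 2 readers × 4 regions = 320 entries over the study. No extra scan, reader or patient is needed. The scores must be entered before each man's unblinded consensus read.
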